
twice a week, together with standard dose lenalidomide and low dose dexamethasone in relapsed or refractory myeloma patients in a phase I/II study with 10 additional patients enrolled at the highest tolerated low azacitidine dose to obtain an initial impression of efficacy and to evaluate whether this dose exerts the expected pharmacodynamic effects in myeloma cells before a larger phase II trial may be conducted. In light of new data supporting use of standard-dose azacitidine in myeloid neoplasia patients with kidney dysfunction(14) and GFR-adjusted lenalidomide for myeloma patients(15), amendment 7 extends the safety and preliminary efficacy evaluations to myeloma patients with GFR 30-59 ml/min (Cockroft-Gault). Lenalidomide will be used at a fixed dose of 10mg daily from day 1-21 every 28 days which yielded equal AUC concentrations in myeloma patients with GFR 30-49m/min as 25mg daily from day 1-21 every 28 days in patients with GFR \geq 80 ml/min in a recent study(15). Only two dose levels of azacitidine will be tested. Dose level "CKD 1" will use azacitidine at 40 mg/m² s.c. twice a week which has been found tolerable in patients with GFR \geq 60 ml/min; one of six patients developed a dose limiting toxicity, culture negative neutropenic fever at an absolute neutrophil count (ANC) nadir of 0.48K/mm³, with resolution the next day at an ANC of 0.89K/mm³ without G-CSF use. At the time of amendment 7, two patients with normal kidney function have completed the first cycle at dose level 5 (azacitidine 50mg/m² s.c. twice a week) without dose limiting toxicities. Six patients with GFR 30-59 ml/min will be treated at CKD 1 if dose limiting toxicities (DLTs) do not occur in more than one patient. If 2 of 3 or 2 of up to six patients develop DLTs at CKD1, subsequent patients will be treated at "CKD -1" (30mg/m² s.c. twice a week). Otherwise (no more than one patient with DLTs at CKD1), subsequent patients will receive azacitidine at 50mg/m² s.c. twice a week (= dose level CKD2). Lower or higher dose levels will not be tested. This modified dose escalation scheme increases safety by enrolling at least 6 patients per dose level and guarantees that the tolerability of twice a week azacitidine in patients with GFR 30-59 ml/min will be defined by enrolling maximally 12 additional patients. Omission of weekly azacitidine is based on the observation that clinical benefit response rates were more than twice as high with twice a week than with weekly azacitidine dosing (40% versus less than 15%) in patients with GFR > 60ml/min, an encouraging result taking into consideration that patients had received a median of 4.5 prior regimens, with myeloma refractory to previous lenalidomide in 88%, to previous proteasome inhibitors in 81%, and to both lenalidomide and proteasome inhibitors in 75%. Once the highest tolerated low dose for patients with reduced GFR (HTLD-CKD) has been defined, enrollment at this dose level may contribute to the 10 patient phase II extension. Before amendment 7 eighteen patients have started treatment, including two at dose level 5. Assuming up to 6 patients will be enrolled per dose level; the maximal number of enrolled patients will therefore increase from previously estimated 40 to 44 after amendment 7.

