5.6.2.3 Combination Therapy

Dosing Schedule for Patients with GFR \geq 60ml/min (Cockroft-Gault)

Dose level	Azacitidine (s.c.)* Starting day 1	Lenalidomide (p.o.) Starting day 1	Dexamethasone (p.o.)
------------	---------------------------------------	---------------------------------------	----------------------

1	30mg/m ² once a week ¹	25mg d1-21 every 28d ³	40mg p.o. once a week ⁴
2	40mg/m ² once a week ¹	25mg d1-21 every 28d ³	40mg p.o. once a week ⁴
3	30mg/m ² s.c. twice a week ²	25mg d1-21 every 28d ³	40mg p.o. once a week ⁴
4	40mg/m ² s.c. twice a week ²	25mg d1-21 every 28d ³	40mg p.o. once a week ⁴
5	50mg/m ² s.c. twice a week ²	25mg d1-21 every 28d ³	40mg p.o. once a week ⁴

* After highest tolerated low dose (HTLD) of azacitidine determination, azacitidine starting dose will be at the HTLD

Dosing Schedule for Patients with GFR 30-59ml/min (Cockcroft-Gault)

Dose level	Azacitidine (s.c.)* Starting day 1	Lenalidomide (p.o.) Starting day 1	Dexamethasone (p.o.)
-1	30mg/m ² s.c. twice a week ²	10mg d1-21 every 28d ³	40mg p.o. once a week ⁴
1	40mg/m ² s.c. twice a week ²	10mg d1-21 every 28d ³	40mg p.o. once a week ⁴
2	50mg/m ² s.c. twice a week ²	10mg d1-21 every 28d ³	40mg p.o. once a week ⁴

* After highest tolerated low dose (HTLD-CKD) of azacitidine determination, azacitidine starting dose will be at the HTLD-CKD

¹ Ideally, azacitidine is administered on the same day each week, but +/- up to two days is allowed, individual doses should be at least 5 days apart. Rotation of injection sites is obligatory.

² Azacitidine should be administered on the same days each week, +/- one day is allowed but there should be at least 48hrs between doses. The following schedules are recommended: Monday-Thursday, Monday-Friday, Tuesday-Friday, Tuesday-Saturday. Rotation of injection sites is obligatory

³: Lenalidomide dosing will be in the evening at approximately the same time each day. Prescriptions must be filled within 7 days. If a dose of lenalidomide is missed, it should be taken as soon as possible on the same day. If it is missed for the entire day, it should not be made up. Patients who take more than the prescribed dose of lenalidomide should be instructed to seek emergency medical care if needed and contact study staff immediately.

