5.7.1 Dose Modification Steps and Dose Re-Escalation Guidelines

5.7.1.1 Dose Modification Steps

Table 1: Lenalidomide dose modification steps for all toxicities listed in Table 5 EXCEPT for renal impairment or toxicities in the presence of renal impairment*

Current Lenalidomide Dose	One Level Dose Reduction
25 mg daily on Days 1-21 every 28 days	20 mg daily on Days 1-21 every 28 days
20 mg daily on Days 1-21 every 28 days	15 mg daily on Days 1-21 every 28 days
15 mg daily on Days 1-21 every 28 days	10 mg daily on Days 1-21 every 28 days
10 mg daily on Days 1-21 every 28 days	5 mg daily on Days 1-21 every 28 days
5 mg daily on Days 1-21 every 28 days	Discontinue lenalidomide

* Renal impairment is defined as calculated creatinine clearance \geq 30mL/min but $<$ 60mL/min (see Table 2 below for lenalidomide dosing)

Table 2: Lenalidomide dose modification steps for renal impairment (see Table 5) and for other toxicities which occur after dose reduction for renal impairment*

Current Lenalidomide Dose	One Level Dose Reduction
25 mg daily on Days 1-21 every 28 days	10 mg daily on Days 1-21 every 28 days
10 mg daily on Days 1-21 every 28 days	15 mg every 48 hours during Days 1-21 every 28 days
15 mg every 48 hours during Days 1-21 every 28 days	5 mg daily on Days 1-21 every 28 days
5 mg daily on Days 1-21 every 28 days	Discontinue lenalidomide

* Renal impairment is defined as calculated creatinine clearance $\geq 30\text{mL/min}$ but $< 60\text{mL/min}$

Table 3: Azacitidine Dose Adjustment Steps

Dose Level +2	100 mg/ m^2 SC twice a week (only for patients on twice a week azacitidine who tolerated azacitidine 75mg/ m^2 SC twice a week but did not respond, see under 5.7.1.2)
Dose Level +1	75 mg/ m^2 SC twice a week (only for patients on twice a week azacitidine who tolerated their full azacitidine starting dose but did not respond, see under 5.7.1.2)
Dose Level 0	Starting azacitidine dose (differs depending on cohort during phase I part, see 5.6.2.3)
Dose Level -1	Reduce dose by 50%, maintain frequency of administration
Dose Level -2	Discontinue azacitidine

Table 4: Dexamethasone Dose Reduction Step

Dose Level – 1	Reduce each dexamethasone dose by 50%
Dose Level – 2	Discontinue dexamethasone

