If the patient's GFR increases from 30-59ml/min at enrollment to ≥ 60 ml/min at the start of a cycle and the previous cycle was tolerated without need for dose reduction of lenalidomide due to any adverse event and no G-CSF or platelet transfusions were required, the dose of lenalidomide may be increased by one dose level according to table 2. If the dose of lenalidomide or azacitidine was reduced due to renal impairment on study, and continued treatment results in calculated creatinine clearance ≥ 60 ml/min (by Cockcroft-Gault), the dose of lenalidomide and azacitidine can be increased by one dose level each at the start of each cycle until the target dose of both drugs is reached provided the calculated creatinine clearance remains ≥ 60 ml/min (by Cockcroft-Gault) and no relationship between study drugs and renal impairment was suspected. If a relationship between study drugs and renal impairment is considered possible, drug increases should be done one drug at a time and alternating between lenalidomide and azacitidine, starting with lenalidomide. Doses may be increased only in patients who completed the previous treatment cycle without dose modifications or treatment delays due to toxicity (regardless of type). Dose increases may occur NOT more frequently than once every 28 days. If the current dose of lenalidomide is 15 mg every 48 hours during Days 1-21 every 28 days, or 5 mg daily on Days 1-21 every 28 days, the first dose increase would be to 10 mg daily on Days 1-21 every 28 days. Additional dose increases if warranted would be in 5 mg increments. After 12 months since initiation of protocol therapy, no further lenalidomide dose titration is permitted.

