5.7.4 Instructions for Initiation of a New Cycle

A new course of treatment may begin on the scheduled Day 1 of a new cycle if:

- The ANC is $\geq 1000/\text{mm}^3$ (G-CSF is allowed to achieve this threshold)
- The platelet count is $\geq 50,000/\text{mm}^3$ (During the first 4 cycles platelet transfusions are allowed to achieve this threshold)
- Any new drug-related neuropathy or rash other than injection site reaction that may have occurred has resolved to \leq grade 1 severity;
- Any bicarbonate decrease below 20mEq/L that may have occurred has resolved to baseline.
- Calculated creatinine clearance $\geq 30\text{ml}/\text{min}$ (by Cockroft-Gault), after 12 cycles on therapy, determining the creatinine clearance every 2 months will suffice
- Any other drug-related adverse events that may have occurred have resolved to \leq grade 2 severity. Physician discretion may be used in initiating the next cycle of treatment if the only toxicities that have not resolved to \leq grade 2 severity are dexamethasone-related toxicities.

If these conditions are not met on Day 1 of a new cycle, the subject will be evaluated weekly and a new cycle of treatment will not be initiated until the toxicity has resolved as described above. If criteria to initiate a new cycle are not met by 21 days after the planned start of a new cycle patients go off study. If a lenalidomide or azacitidine dose reduction was taken during the previous cycle, and the cycle was completed without requiring further dose modification, then the next cycle will start at the same reduced dose. **If lenalidomide and / or azacitidine dosing was omitted for the remainder of the previous cycle or if the new cycle is delayed due to toxicity newly encountered on the scheduled Day 1**, then the new cycle will be started with a one-level dose reduction of lenalidomide and/or azacitidine as appropriate. Dose reductions should generally be taken one drug at a time based on attribution of toxicity to one of the drugs unless otherwise indicated in Section 5.7.3.

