5.7.5 Instructions for Dose Modifications or Interruption During a Cycle

Table 5 outlines instructions for dose reductions of study drugs for specific toxicities. Study drugs may be temporarily or permanently dose reduced using doses outlined in table 1-4 or temporarily discontinued in other situations where their continued administration according to protocol is felt unsafe by the treating physician.

Table 5: Dose Modifications Azacitidine and Lenalidomide

NCI CTC Toxicity Grade	Dose Modification Instructions
Grade 3 neutropenia associated with fever (temperature $\geq 38.5^{\circ}$ C) or Grade 4 neutropenia	
 • Hold (interrupt) lenalidomide and, while on combination, also azacitidine dose. • Follow CBC weekly. • During combination therapy with lenalidomide and azacitidine: 
 ◦ If neutropenia has resolved to \leq grade 2 prior to Day 21 of the current cycle, restart azacitidine at the next lower dose level and continue lenalidomide at the same dose level if the patient's myeloma has not previously been refractory to lenalidomide, otherwise maintain azacitidine dose level and reduce lenalidomide by one dose level (if the patient is only on one of these drugs reduce its dose by one level) and continue treatment through the scheduled end of the cycle. Otherwise, omit treatment for the remainder of the cycle and reduce dose levels in the same way at the start of the next cycle. Omitted doses are not made up. ◦ If neutropenia is the only toxicity for which a dose reduction is required (no fever or other reason to reduce doses), G-CSF should be considered instead of a dose reduction. • During maintenance therapy with lenalidomide: 
 ◦ If neutropenia has resolved to \leq grade 2 prior to Day 21 of the current cycle, restart lenalidomide at the next lower dose level, and continue through the scheduled end of the cycle. Otherwise, omit lenalidomide for the remainder of the cycle and reduce lenalidomide by 1 dose level at the start of the next cycle. Omitted doses are not made up.

Table 5: Dose Modifications Azacitidine and Lenalidomide

NCI CTC Toxicity Grade	Dose Modification Instructions

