Venous thrombosis/embolism \geq Grade 3	
 Hold (interrupt) lenalidomide and start anticoagulation; restart lenalidomide at investigator's discretion (maintain dose level). Omit lenalidomide for remainder of cycle. See Anticoagulation (Section 5.8.1.2)
Hyperthyroidism or hypothyroidism	
 Omit lenalidomide for remainder of cycle, evaluate etiology, and initiate appropriate therapy. See Instructions for Initiation of a New Cycle and reduce the dose of lenalidomide by 1 lenalidomide dose level.
Bicarbonate - low (CO₂ below 20mEq/L)	
 If unexplained hold azacitidine and lenalidomide Check weekly Upon recovery to baseline restart azacitidine at next lower dose level and restart lenalidomide at the current dose. If recovery to baseline occurs prior to Day 21 of the current cycle, restart as instructed above and continue treatment through the scheduled end of the cycle. Otherwise, omit treatment for remainder of cycle and reduce the dose of azacitidine by 1 dose level and maintain the current dose of lenalidomide at the start of the next cycle. Omitted doses are not made up.

Table 5: Dose Modifications Azacitidine and Lenalidomide

NCI CTC Toxicity Grade	Dose Modification Instructions
Renal impairment (Calculated creatinine clearance \geq 30ml/min < 60ml/min)	
 Maintain current dosing schedule, but reduce lenalidomide by 1 dose level (see Section 5.7.1, Table 2). If lenalidomide dose had been \geq 15mg, reduce to 10mg daily on Days 1-21 of each 28-day cycle.

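### The Table 5 renal row (clearance 30 to below 60) has no exemption for patients enrolled at GFR 30-59: read literally, it cuts their assigned lenalidomide 10 mg, and 5.7.3 restores it only at 60 or more

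*Combined protocol and SAP*

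**What the plan says.** The Synopsis text for amendment 7 sets the dose for the reduced-GFR cohort: "Lenalidomide will be used at a fixed dose of 10mg daily from day 1-21 every 28 days". The dosing table for GFR 30-59 in 5.6.2.3 gives the same dose at all three azacitidine levels.

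Section 5.7.5 opens with "Table 5 outlines instructions for dose reductions of study drugs for specific toxicities". For calculated clearance of at least 30 but below 60, the table says "Maintain current dosing schedule, but reduce lenalidomide by 1 dose level (see Section 5.7.1, Table 2"). A second sentence in that row sends any dose of 15 mg or more to 10 mg daily. Nothing is said about a patient already on 10 mg. In Table 2 (5.7.1.1) the step below 10 mg daily is "15 mg every 48 hours during Days 1-21 every 28 days".

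Under 5.7.4, if a reduced cycle is completed without further modification, "then the next cycle will start at the same reduced dose".

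The way back is in 5.7.3: "If the dose of lenalidomide or azacitidine was reduced due to renal impairment on study, and continued treatment results in calculated creatinine clearance" of 60 ml/min or more, doses may go up one level per cycle while clearance stays there. In the same paragraph, for patients on 15 mg every 48 hours or 5 mg daily, "the first dose increase would be to 10 mg daily on Days 1-21 every 28 days". The one sentence written for patients enrolled at 30-59 also requires 60 or more, and it concerns going above 10 mg.

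**The concern.** The row's trigger is the cohort's eligibility range. A rule suited to patients enrolled at 60 or more on 25 mg, for whom entering the band is a change and 10 mg is the right landing point, also reaches patients who start in the band on 10 mg. For them it prescribes a dose the plan elsewhere reserves for worse renal function. The condition for undoing it is a clearance higher than any of them had at enrolment.

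At stake is the lenalidomide dose actually delivered from cycle 2 onward. The plan will describe response after 6 and 12 cycles, progression-free survival and later-cycle toxicity in this cohort. If sites read the row differently, patients with the same clearance will receive different lenalidomide doses, and the reports will not show why.

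**Working it through.** The plan states no delivered-dose figure, so there is nothing to reproduce. The check sets the rules side by side and then works out the dose.

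**Lenalidomide dose by clearance, as each section gives it**

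| Situation | Source | Lenalidomide, days 1-21 |
|---|---|---|
| Enrolled at 30-59 | Synopsis; 5.6.2.3 | 10 mg daily |
| 30 to below 60, full prior dose | 5.2.2, item 9 | 10 mg daily |
| Below 30, no dialysis, full prior dose | 5.2.2, item 9 | 15 mg every 48 h |
| 30 to below 60 on study, current dose 15 mg or more | Table 5 | 10 mg daily |
| 30 to below 60 on study, current dose 10 mg | Table 5 with Table 2 | 15 mg every 48 h |

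The last line is out of step with the others. At a clearance of 40, a patient enrolled at 60 or more on 25 mg goes to 10 mg, while a patient enrolled in the band on 10 mg goes below it. The pharmacokinetic study described in 5.1.1.3 supports 10 mg most directly at GFR 30-49 (average daily AUC 103% of the reference group) and used 15 mg every other day below 30.

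**Routes back to 10 mg**

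- The renal part of 5.7.3 needs 60 or more.
- The hematologic part of 5.7.3 applies only to hematologic reductions.
- Maintenance titration in 5.6.2.4 is discretionary, open only to patients below PR, and stops 12 months after starting therapy.

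None of these restores 10 mg within the band during combination therapy. Patients at PR or better have no stated route in maintenance either.

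**Dose per cycle**

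- Assigned: 10 × 21 = 210 mg.
- 15 mg on days 1, 3, ..., 21: 11 × 15 = 165 mg; 165/210 = 0.786, or -21%.
- If the alternate-day schedule gives only 10 doses: 150 mg, or -29%.

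**Six cycles, one unreversed step at 165 mg (assigned 6 × 210 = 1260 mg)**

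| Cut from cycle | Total, mg | % of assigned |
|---|---|---|
| 2 | 210 + 5 × 165 = 1035 | 82 |
| 3 | 420 + 4 × 165 = 1080 | 86 |
| 4 | 630 + 3 × 165 = 1125 | 89 |
| 5 | 840 + 2 × 165 = 1170 | 93 |
| 6 | 1050 + 165 = 1215 | 96 |

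**Inside cycle 1.** Note 4 to the Section 2 schedule places calculated clearance at baseline and at each cycle start. A mid-cycle cut arises only if a site calculates clearance from the weekly metabolic panel. A cut at day 8 gives 70 + 7 × 15 = 175 mg (-17%); at day 15, 140 + 4 × 15 = 200 mg (-5%).

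**With the proposed wording.** No cut occurs in the band, so 1260 mg is planned. A patient already cut for one cycle and then restored receives 1260 - 45 = 1215 mg (96%); for two cycles, 1260 - 90 = 1170 mg (93%).

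**The case against.** The best defence is that the row was never meant for these patients. Table 5 is introduced as a toxicity table, and a patient whose baseline already meets the definition of renal impairment has had no new event at a clearance of 40. The row's second sentence, exclusion criterion 9 and 5.6.2.3 all point to 10 mg as the dose for the band. The Table 2 step below 10 mg has other uses: clearance below 30, and other toxicities after a renal reduction. Section 5.7 calls its contents recommended steps and allows clinical judgment. A sensible site would probably keep such a patient on 10 mg.

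Much of that stands as evidence of intent, and many sites may act on it. It does not settle the text. Clinical judgment is offered for scenarios the tables do not cover, and this row covers the band by its numbers. No footnote or sentence excludes patients enrolled in it. If the intent is 10 mg, saying so costs nothing.

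Some stronger readings are not supported:

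- A reader might infer that a fall within the band, say 55 to 40, is the trigger. The row is keyed to being in the band and mentions no fall.
- A reader might infer that the whole cohort is cut on day 1 and stepped down every cycle. The starting dose is set by 5.6.2.3, and 5.7.4 carries a reduced dose forward unchanged. The documents do not show that such a cascade is intended or would happen.
- A reader might call the threshold of 60 an error after a dip below 30 as well. Lenalidomide is about two-thirds excreted unchanged in urine, and renal impairment raises exposure (5.1.1.3), so slow re-escalation there, including whether halved azacitidine stays halved, is a defensible safety trade-off.

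**Conclusion.** The conflict holds as a matter of wording. The row, followed as written, contradicts the cohort's fixed 10 mg dose, and the renal re-escalation rule gives these patients no way back at their own baseline clearance. Where a site applies the row once, planned lenalidomide is 21% lower per cycle and 82% to 96% of the six-cycle total, depending on when the cut is made. These figures assume one step, 11 alternate-day doses, full adherence and no other modification.

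The cohort-level effect cannot be sized. Up to 12 phase I patients plus any in the extension are exposed to the rule, but the documents do not say how many would be cut or how sites read the row.

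A reader might infer that the HTLD-CKD decision or an efficacy conclusion is compromised. The documents do not support that. DLT is counted in cycle 1, before the next scheduled clearance can act. Response and survival are descriptive, with no test or threshold, and delivered dose already varies by design, for example through azacitidine escalation in 5.7.2. This is a dosing rule to correct, not a threat to the primary endpoint.

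**What to change.** In the Table 5 row for clearance 30 to below 60, state that lenalidomide is reduced to, but not below, 10 mg daily, so patients enrolled at GFR 30-59 stay on 10 mg.

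In 5.7.3, state that a patient enrolled at 30-59 who was cut below 10 mg under this row may return to 10 mg at the start of a cycle while clearance is in the 30-59 band, under the section's existing condition that the previous cycle was free of toxicity-related modification or delay. Once the floor is in place, this sentence serves only patients already cut.

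Keep 60 as the trigger for doses above 10 mg and for patients enrolled at 60 or more. Re-escalation after a fall below 30, and whether azacitidine then stays halved, remain the sponsor's decision.

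The cost is two sentences in an amendment. No new data are needed: clearance at each cycle start (Section 2, note 4) and dosing records (5.6.2.2) are already collected.
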